3.1 Study population/Patient Enrollment

Eligibility criteria - Inclusion:

Pediatric patients 0-18 of age will be recruited by our surgical colleagues based on the clinical concern for craniosynostosis and possible need for calvarial reconstruction. Study Team will also review the surgical calendars and Mayo Clinic data base (MDE, i2b2) searching for potential pediatric patients. When a patient is found they will email the surgeons for a review and verification of qualification for the study. Patients must have gotten a clinically indicated CT within a 6 week time period from the ZTE MRI.

Eligibility criteria - Exclusion:

Exclusion criteria include lack of consent, clinical CT scan of the head, contraindication/inability to undergo both examinations within the designated time period and/or undiagnostic image quality. Pregnancy (women of childbearing age will be given a urine pregnancy test).

Patients will undergo ZTE within a 6 week time period from the CT scan (though attempting with each patient to schedule on the same day). ZTE MRI examinations will be added, when possible, to a patient's already scheduled MRI or will take place as a standalone appointment without sedation.

Patient preparation

A Review Preparatory to Research will be conducted by the study coordinators to determine if the patient meets inclusion criteria including a pre-screen for MRI safety.

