Comparative Analysis of Zero Echo-time MRI and CT for Pediatric Craniosynostosis

NCT#04704284

23May2022

Title of the Study: Comparative analysis of zero echo-time MRI and CT for pediatric craniosynostosis. Ver 3 May 23, 2022.

Principle Investigator: [name] Neuroradiology

Abstract

Zero echo-time (ZTE) MRI (K132376) is an emerging technique that has been shown to adequately image bone and will likely allow eventual widespread imaging of osseous structures. The opportunity to exchange standard CT evaluation for a radiation-free modality is desirable, particularly in the pediatric population. A promising clinical application is the use of ZTE for diagnosing craniosynostosis, potentially precluding the use of the standard volumetric head CT scan. We propose a comparative analysis between zero echo-time MRI and CT to assess their effectiveness in diagnosing this entity. Our hypothesis is that ZTE is concordant with CT for suture visualization and imaging diagnosis, permitting its use in the clinical setting for this purpose.

Research Plan

1. Specific Aims

To establish whether ZTE imaging of the infant calvarium can provide equivalent information to CT and allow for a reliable diagnosis of craniosynostosis in a child. This aim is based on the hypothesis that there will be 90% or greater concordance between ZTE and CT findings.

2. Background & Significance

Magnetic resonance imaging (MRI) has become the primary workhorse for pediatric neuroradiology, providing superior imaging of soft tissues in the brain, head, neck and spine, while offering the added benefit of having no ionizing radiation. Evaluating cortical bone, however, continues to be a limitation with conventional MRI sequences. The contents within cortical bone (inorganic minerals, collagen matrix and various water concentrations) and their tightly organized structure result in very short T2 values ($T2 \sim 300-400 \,\mu s$) and rapid magnetization decay which yield signal voids and insufficient image contrast.

Computed tomography (CT), therefore, continues to be the primary modality for evaluating osseous structures. This modality is not ideal in children who have increased sensitivity to the adverse effects of radiation. Developing a comparable MR sequence which can evaluate bone without radiation is critical and aligns with the ALARA ("as low as reasonably achievable") radiation safety principle to minimize radiation doses in children.

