3.2 Patient Scanning Protocol

CT examinations will include age-appropriate protocols for radiation dose minimization, with three-dimensional reconstruction, per the cranisynostosis protocol. MR imaging will be performed on a 3T scanner capable of ZTE imaging. The pediatric whole-head ZTE protocol is set up to acquire volumetric proton density-weighted images with the following acquisition parameters: TE 0.016ms, field-of-view 18×18 cm, readout matrix 180×180, number of slices 180, slice thickness 1 mm, bandwidth 31.25kHz, flip angle 2°. The image resolution is 1-mm isotropic and therefore can be reformatted in any plane. The acquisition time for each acquisition is approximately 2 minutes. The acquisition is repeated to achieve better SNR by averaging the two acquisitions during post-processing offline after rigid body registration. In case significant motion is observed in one of the acquisitions, only the acquisition with less motion will be used during post-processing to generate the bright-bone images. An adjunct 3D GRE sequence will be made available to aid with differentiating between cortical bone and soft tissue. The acquisition parameters for the axial 3D GRE sequence are: TR 6.8ms, TE 2.3ms ("in phase"), flip angle 5-degree, field-of-view: 18X18 cm, acquisition matrix 256 X 256, slice thickness 1mm. The scan time for the 3D GRE sequence is ~6 minutes.

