3.3 MRI and CT evaluation

Four CAQ certified neuroradiologists will independently evaluate CT and ZTE images in separate sessions. There will be at least a two-week time window between readings of CT and ZTE to diminish recall bias. ZTE data will be presented in three display formats: (1) raw magnitude image with multiplanar reformats, (2) bright-bone reconstructions, (3) 3D volume renderings. CT data will be presented in two display formats: (1) source images with multiplanar reformats and (2) 3D volume renderings. The images will be reviewed in a blinded fashion during separate interpretation sessions to prevent recall bias.

3.4 Data Collection:

Each observer will provide ordinal ratings with regard to (a) visibility of each major cranial suture and fontanelles [1 = poorly seen, 2 = partially seen, 3 = fully seen] and (b) confirmation of diagnosis based on the clinical question [+1 = pathologic abnormality present, 0 = unable to tell, -1 = pathologic abnormality absent].

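### The image-quality exclusion names no modality, so as written it permits nondiagnostic ZTE scans to be dropped uncounted, leaving any ZTE-CT concordance conditional on a readable ZTE

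*Combined protocol and SAP*

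**What the plan says.** The exclusion criteria in section 3.1 include "contraindication/inability to undergo both examinations within the designated time period and/or undiagnostic image quality". The criterion gives no modality, assessor, threshold or time point for judging image quality.

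The other relevant statements are:

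- **Aim and use.** Section 1 hypothesises that "there will be 90% or greater concordance between ZTE and CT findings". The Abstract presents ZTE as "potentially precluding the use of the standard volumetric head CT scan".
- **Order of scans.** The inclusion criteria in section 3.1 state: "Patients must have gotten a clinically indicated CT within a 6 week time period from the ZTE MRI". The ZTE is a study procedure done within six weeks of the CT, on the same day where that can be arranged.
- **Setting of the ZTE.** Section 3.1: "ZTE MRI examinations will be added, when possible" to an MRI that is already booked; otherwise the scan "will take place as a standalone appointment without sedation".
- **Motion.** Section 3.2: "In case significant motion is observed in one of the acquisitions, only the acquisition with less motion will be used during post-processing".
- **Ratings.** In section 3.4 readers score "visibility of each major cranial suture and fontanelles [1 = poorly seen, 2 = partially seen, 3 = fully seen", and score the diagnosis as present, absent or unable to tell.
- **Analysis.** Section 3.5 plans an interobserver kappa with 95% confidence intervals, based on 37 patients. It does not mention scans that were excluded, abandoned or unreadable.

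**The concern.** A ZTE that gives no answer cannot stand in for the CT, so failure to give an answer is part of the performance of the test under study. The quality of the ZTE is known only after it has been acquired. If the exclusion is applied to the ZTE, patients leave the study because of the result of the test being evaluated. The question then shifts from whether ZTE can replace CT to whether ZTE agrees with CT when it works, and the shift can only favour ZTE.

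Failures are foreseeable: standalone scans are unsedated, and section 3.2 itself plans for significant motion. If excluded patients are not counted, a reader of the final report cannot tell whether this happened to none of the children or to several.

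**Working it through.** **1. The passages side by side.** The only examinations named in the exclusion clause are the two together, so the wording does not confine image quality to the CT. The eligibility setting and the tense of the inclusion criterion point towards the CT, which may already exist at enrolment. Both readings are open.

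**2. Whether other sections close the gap.** The motion rule in section 3.2 is written for motion in one of the two acquisitions; it does not cover both being degraded, or an abandoned scan. The poorly-seen and unable-to-tell ratings in section 3.4 record failures only for scans that reach the readers. No section draws the line between a scan that is rated unable to tell and one that is excluded.

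**3. The plan's own figure.** The documents give no failure rate and no concordance calculation to reproduce. The one relevant number is 37, the sample size for kappa. It cannot be reproduced uniquely, because the sidedness of the test and the probability of the third rating level are not stated. A goodness-of-fit calculation for four raters (kappa 0.95 against 0.70, alpha 0.05, 80% power) gives 51 two-sided or 41 one-sided with 80/20 taken as two levels, and 38 two-sided with an assumed 70/20/10 split. So 37 is not shown to be wrong, and it serves below only as a scale.

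**4. Effect on concordance.** Let c be concordance among readable scans and f the fraction of ZTE scans that fail. Both are assumptions. Counting failures as non-concordant:

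- overall concordance = c × (1 − f)
- it falls below 90% when f > 1 − 0.90/c

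| c (assumed) | break-even f | overall at f = 2% | at f = 5% | at f = 10% |
|---|---|---|---|---|
| 95% | 1 − 0.90/0.95 = 5.3% | 93.1% | 90.2% | 85.5% |
| 97% | 1 − 0.90/0.97 = 7.2% | 95.1% | 92.2% | 87.3% |
| 100% | 1 − 0.90/1.00 = 10.0% | 98.0% | 95.0% | 90.0% |

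**5. The same in patients**, with one call per patient. Section 3.5 does not say whether 37 means scanned or analysed.

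- 37 analysed, failures uncounted: 34/37 = 91.9% becomes 34/38 = 89.5% with one failure; 35/37 = 94.6% becomes 35/39 = 89.7% with two; 37/37 becomes 37/42 = 88.1% with five.
- 37 scanned, every readable pair concordant: three failures give 34/37 = 91.9%, four give 33/37 = 89.2%.

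**6. Precision of the failure rate.** With no failures in 37, the exact 95% upper limit is 1 − 0.025^(1/37) = 9.5%.

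**The case against.** The strongest defence is that the phrase concerns the CT. It sits under eligibility, the CT is described as already done and the ZTE as still to come, and where the CT comes first it is the only image that can be judged at enrolment. This has real weight. It does not settle the matter, because same-day scanning is attempted and the clause speaks of both examinations.

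A reader might infer that the investigators plan to discard failed ZTE scans, or that the concordance will be overstated. The documents support neither. No section describes removing scans before reading, and the ratings in section 3.4 show that some poor images are expected to reach the readers.

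A reader might also take the inability criterion as a second route for dropping failed ZTE scans. It is qualified by the designated time period and paired with contraindication, so it reads mainly as safety or scheduling, and a failed attempt could be repeated within the six weeks. I do not rest the point on it.

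Finally, one or two failures crossing 90% should not be read as overturning a planned conclusion. Section 3.5 sets no test against 90%. The shift is also small against sampling error: the exact 95% interval is 78.1% to 98.3% for 34/37 and 75.2% to 97.1% for 34/38. Restricting concordance to readable pairs is a legitimate choice, provided that failures are reported beside it. What stands is that the plan does not require them to be.

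**Conclusion.** The point holds as a conditional one and should be fixed. The criterion is ambiguous. On one permitted reading it removes failures of the test under study after the fact, and nothing in the plan would bring this to light. The direction of the bias would favour ZTE. Its size is unknown: negligible if almost every ZTE is readable, and enough to move an overall figure below 90% if failures exceed roughly 5% to 10%, for readable-scan concordance of 95% to 100%. That range rests on assumed values of f and c and on counting failures as non-concordant. Confidence is medium, because the CT-only reading may be what was meant; if so, rewording the criterion settles the image-quality exclusion, and the counting of ZTE failures still has to be added.

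**What to change.** 1. Reword the image-quality exclusion in section 3.1 so that it applies only to a nondiagnostic CT, naming the assessor and threshold. State that no patient is removed because an attempted ZTE was nondiagnostic or not completed.
2. Have the four readers rate every acquired ZTE, using the unable-to-tell rating where needed. Record abandoned ZTE scans as nondiagnostic, without imputed ratings.
3. Keep a log of all consented patients. Report the number excluded or nondiagnostic by modality and reason, including patients screened out on CT quality before any ZTE. A log of attempted ZTE scans alone would undercount CT failures.
4. Wherever ZTE-CT concordance is reported, give it for all attempted ZTE scans with a definite CT call (nondiagnostic ZTE counted as non-concordant) and, beside it, for readable pairs only.

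Interobserver kappa stays as planned, on actual reader ratings. Section 3.5 contains no ZTE-CT concordance analysis; designing one is a separate matter.

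The cost is a reworded criterion, a log and a short SAP paragraph. No extra readers are needed, and the coordinator already has contact with each patient before scanning (section 3.6). The downsides are that headline concordance may be lower, readers will spend some time on poor scans, and the failure rate will be imprecise at this sample size.

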3.2 Patient Scanning Protocol

CT examinations will include age-appropriate protocols for radiation dose minimization, with three-dimensional reconstruction, per the cranisynostosis protocol. MR imaging will be performed on a 3T scanner capable of ZTE imaging. The pediatric whole-head ZTE protocol is set up to acquire volumetric proton density-weighted images with the following acquisition parameters: TE 0.016ms, field-of-view 18×18 cm, readout matrix 180×180, number of slices 180, slice thickness 1 mm, bandwidth 31.25kHz, flip angle 2°. The image resolution is 1-mm isotropic and therefore can be reformatted in any plane. The acquisition time for each acquisition is approximately 2 minutes. The acquisition is repeated to achieve better SNR by averaging the two acquisitions during post-processing offline after rigid body registration. In case significant motion is observed in one of the acquisitions, only the acquisition with less motion will be used during post-processing to generate the bright-bone images. An adjunct 3D GRE sequence will be made available to aid with differentiating between cortical bone and soft tissue. The acquisition parameters for the axial 3D GRE sequence are: TR 6.8ms, TE 2.3ms ("in phase"), flip angle 5-degree, field-of-view: 18X18 cm, acquisition matrix 256 X 256, slice thickness 1mm. The scan time for the 3D GRE sequence is ~6 minutes.

3.3 MRI and CT evaluation

Four CAQ certified neuroradiologists will independently evaluate CT and ZTE images in separate sessions. There will be at least a two-week time window between readings of CT and ZTE to diminish recall bias. ZTE data will be presented in three display formats: (1) raw magnitude image with multiplanar reformats, (2) bright-bone reconstructions, (3) 3D volume renderings. CT data will be presented in two display formats: (1) source images with multiplanar reformats and (2) 3D volume renderings. The images will be reviewed in a blinded fashion during separate interpretation sessions to prevent recall bias.

3.4 Data Collection:

Each observer will provide ordinal ratings with regard to (a) visibility of each major cranial suture and fontanelles [1 = poorly seen, 2 = partially seen, 3 = fully seen] and (b) confirmation of diagnosis based on the clinical question [+1 = pathologic abnormality present, 0 = unable to tell, -1 = pathologic abnormality absent].

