Three dimensional proton density-weighted zero echo-time (ZTE) is a developing technique that uses proton density differences rather than T2 relaxation time differences to achieve contrast. It has been used to better image bone structure within the calvarium, spine and

extremities¹⁻⁵ and has been explored for use in attenuation correction for PET/MR studies⁶⁻⁸. The sequence is performed without preparation pulses or multiple echoes, rendering it time-efficient and (if performed alone), usually precluding the need for sedation¹. Alternatively, it can easily be added to a more complete MR exam, providing an efficient "one stop" evaluation.

The diagnostic utility of ZTE is not yet established and a comparative validation study of ZTE with CT is needed before reliably using this in the clinical setting for preoperative purposes. If ZTE is shown to be non-inferior to CT for evaluation of craniosynostosis, clinical practice will be substantially improved; neurosurgeons as well as parents and children may be offered a radiation free imaging tool. This is particularly advantageous for this population of children which may require multiple follow-up exams after surgical correction. Moreover, this could serve as an initial study preceding evaluation of other osseous structures including facial bones and skull base. The findings in this study could also drive further technological advancements to include the creation of surface renderings based on ZTE data for anatomic modeling.

3. Study Design

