3.5 Data Analysis

Sample size estimation for this interobserver agreement study was based on a confidence interval approach⁹. Using 4 raters and 3 levels of rating for their assessment, with type I error (alpha) fixed at 0.05 and an expected 80/20 probability of the absence or presence of craniosynostosis, respectively, we will have 80% power to claim the interobserver kappa statistics is greater than 0.7 when the true kappa is 0.95 with a sample size of 37

patients. Interobserver agreement will be summarized by the kappa coefficient statistic and corresponding 95% confidence intervals.

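### Section 3.4 does not record which suture is judged fused, so the ratings cannot show that ZTE and CT identify the same abnormal suture

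*Combined protocol and SAP*

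**What the plan says.** Section 3.4 (Data Collection) lists two ratings per observer. The first is "visibility of each major cranial suture and fontanelles [1 = poorly seen, 2 = partially seen, 3 = fully seen", made structure by structure. The second is "confirmation of diagnosis based on the clinical question", with three levels: +1 for abnormality present, 0 for cannot tell, -1 for abnormality absent. The per-structure wording belongs only to the first. Section 3.5 bases the sample size on an "expected 80/20 probability of the absence or presence of craniosynostosis" and counts patients, so the second rating is most naturally read as one call per patient.

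Section 3.1 describes recruitment on a general suspicion of craniosynostosis and mentions no particular suture. Sections 3.3 and 3.6 provide for blinded reading of images without identifiers. Neither says what the clinical question contains or whether it is displayed.

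Section 1 asks whether ZTE "can provide equivalent information to CT" and hypothesizes that "there will be 90% or greater concordance between ZTE and CT findings". The Abstract's hypothesis is that "ZTE is concordant with CT for suture visualization and imaging diagnosis". Section 2 says the comparison is needed "before reliably using this in the clinical setting for preoperative purposes".

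**The concern.** A +1 says that something is abnormal, not where. Unless the clinical question fixes the suture, a reader can give +1 on CT for one suture and +1 on ZTE for a different one, and the pair counts as concordant. Two readers can agree in the same empty way. If the question does name a suture and readers see it, this mismatch disappears, but fusion at any other suture is still not recorded.

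The visibility score does not fill the gap. It allows a suture-by-suture comparison of how well structures are seen, but a low score is not a fusion call. Excluding non-diagnostic images (section 3.1) and dropping the acquisition with more motion (section 3.2) make poor image quality a less likely cause of a low score. Age-expected closure remains another, because section 3.1 states "Pediatric patients 0-18 of age will be recruited by our surgical colleagues".

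At stake is the wider part of the aim. Equivalence of information, and use before surgery, call for knowing that both modalities point to the same suture. An entry not made at the read cannot be recovered by analysis, only by reading again.

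**Working it through.** **Inputs.** From section 3.5: N = 37, 4 raters, 20% presence, null kappa 0.7, true kappa 0.95, alpha 0.05, power 80%. From section 1: the 90% concordance target. Assumed for illustration: 7 positives (0.20 × 37 = 7.4), full agreement on presence or absence, and disagreement only on which suture.

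**The plan's own figure.** I used a goodness-of-fit calculation with a beta-binomial model (4 raters, prevalence 0.20). The probabilities of 0, 1, 2, 3 or 4 positive ratings are:
- kappa 0.7: 0.7073, 0.0725, 0.0504, 0.0522, 0.1175
- kappa 0.95: 0.7852, 0.0109, 0.0081, 0.0104, 0.1855

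The sum of (difference)²/(probability at 0.7) is 0.1695. One-sided, N = (1.645 + 0.842)²/0.1695 = 36.5, so 37. The two-sided version gives 46.3, so 47. The plan does not state sidedness. The stated N can be reproduced, and the present point does not depend on it.

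**ZTE-CT agreement, one reader.** With m different-suture cases, same-suture concordance is (37 - m)/37 over all patients and (7 - m)/7 among the positives. Intervals are exact (Clopper-Pearson) 95%.

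| m | Recorded rating | Same suture, all 37 | Same suture, 7 positives |
|---|---|---|---|
| 1 | 100% | 97.3% (85.8-99.9) | 85.7% (42.1-99.6) |
| 2 | 100% | 94.6% (81.8-99.3) | 71.4% (29.0-96.3) |
| 3 | 100% | 91.9% (78.1-98.3) | 57.1% (18.4-90.1) |
| 4 | 100% | 89.2% (74.6-97.0) | 42.9% (9.9-81.6) |

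The overall point estimate falls below 90% only at m = 4, that is 4/7 = 57% of positives. Section 3.5 defines no ZTE-CT concordance statistic, so this column answers the aim in section 1 rather than a planned analysis.

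**Interobserver kappa, the statistic that is planned.** Suppose the four readers all give +1 in the 7 positives but split 2/2 between two sutures in q of them. In a split patient 2 of 6 reader pairs agree. For a suture-specific rating:
- observed agreement: Po = 1 - (2q/3)/37
- chance agreement: Pe = [30² + (7 - q/2)² + (q/2)²]/37²
- kappa = (Po - Pe)/(1 - Pe)

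| q | Po | Pe | Suture-specific kappa | Kappa on the recorded item |
|---|---|---|---|---|
| 1 | 0.982 | 0.688 | 0.94 | 1.00 |
| 3 | 0.946 | 0.681 | 0.83 | 1.00 |
| 5 | 0.910 | 0.677 | 0.72 | 1.00 |
| 6 | 0.892 | 0.676 | 0.67 | 1.00 |

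The suture-specific value drops below 0.7 only when 6 of 7 positives split. At every q the recorded item stays at 1.00, so the planned data would not reveal the mismatch.

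**The case against.** The strongest reply is that the recorded items match the stated hypothesis. The Abstract speaks of visualization and imaging diagnosis: the visibility score covers one and the +1/0/-1 rating the other. Fusion site is nowhere named as an endpoint. This stands as far as it goes, and the presence/absence analysis is sound on its own terms. It does not meet the wider wording in sections 1 and 2 on equivalent information and preoperative use.

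A second reply is that readers must see the clinical question, since they are asked to confirm a diagnosis against it. The blinding in section 3.3 is explained by recall bias, and removing identifiers does not mean hiding the indication. This largely stands. A reader might infer from the blinding that the question is withheld, but the documents do not support that. What remains open is mainly whether the question names a suture.

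Third, large effects need mismatch rates that nothing in the documents suggests: 4 of 7 positives for concordance, or 6 of 7 for kappa. That is correct. A reader might infer that the diagnosis agreement will be inflated, or that the 90% hypothesis would fail. Neither follows.

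Last, the reading form is not in the documents, and section 3.4 describes ordinal ratings, so a location field could exist without being listed. That is possible, and one sentence would settle it.

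**Conclusion.** The gap in the listed data is definite; its effect is unknown and may be zero. It is zero if the question names a suture, readers see it and no other suture is fused, or if readers in practice always agree on the site. As planned, the ratings support agreement on visualization and on presence or absence. They cannot show that ZTE and CT identify the same abnormal suture(s).

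The figures are illustrations. They rest on the plan's 20% prevalence, on perfect presence/absence agreement and, for kappa, on even 2/2 splits. More positives than planned would leave more room for mismatch and give narrower intervals.

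Nothing here shows that N = 37 or the planned kappa is wrong for the rating it was built on. Nor does the gap require a full fusion call on every suture: with about 7 positives that would be more than the defect needs. This should be corrected before reading starts, because the change is cheap then and expensive later. It does not undermine the presence/absence result.

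**What to change.** In section 3.4:
- Whenever a reader gives +1 on either modality, record the suture(s) judged pathologically fused.
- State whether the clinical question names a suture and whether readers are shown it. If it does name one, also say how a reader rates fusion found only at another suture.
- If the reading form already records the suture, say so; that settles the data-collection part.

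In section 3.5, report descriptively with exact 95% confidence intervals how often ZTE and CT +1 ratings name the same suture(s), reader by reader, and how often readers' +1 ratings do so. Count the between-reader result by patient, because reader pairs within a patient are not independent. Keep the visibility score, the diagnosis rating, the planned kappa and N = 37.

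Cost: one entry per positive read. With 7 positives that is 7 × 2 × 4 = 56 entries, or 14 per reader. If ratings are made for each of the five display formats in section 3.3, which the plan does not say, it is 7 × 5 × 4 = 140, or 35 per reader. Reported concordance may be lower, and the intervals will be wide, so this is an estimate and not a test. Adding the entry afterwards would mean repeating up to 37 × 2 × 4 = 296 reads, again with the two-week gap.
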